8.4.7 Events of Clinical Interest

Selected serious and nonserious AEs are also known as ECIs and must be reported to the Sponsor.

Events of clinical interest for this study include:

1. An elevated AST or ALT laboratory value that is greater than or equal to 3X the ULN and an elevated total bilirubin laboratory value that is greater than or equal to 2X the ULN and, at the same time, an alkaline phosphatase laboratory value that is less than 2X the ULN, as determined by way of protocol-specified laboratory testing or unscheduled laboratory testing.*

*Note: These criteria are based on available regulatory guidance documents. The purpose of the criteria is to specify a threshold of abnormal hepatic tests that may require an additional evaluation for an underlying etiology. The study-site guidance for assessment and follow-up of these criteria can be found in the Investigator Study File Binder (or equivalent).

8.5 Treatment of Overdose

In this study, an overdose is the receipt of any number of capsules greater than the number of capsules to be taken as outlined in the pharmacy manual.

No specific information is available on the treatment of overdose.

Decisions regarding dose interruptions or modifications will be made by the investigator in consultation with the Sponsor Clinical Director based on the clinical evaluation of the participant.

8.6 Pharmacokinetics

PK parameters will not be evaluated in this study.

8.7 Pharmacodynamics

Virologic, clinical efficacy, and clinical safety endpoints (Section 3) will be summarized. For assessment of antiviral activity of MOV, baseline and postdose virologic information (eg, viral RNA) from NP swabs of participants will be measured at prespecified timepoints in the SoA (Section 1.3.1). For each participant, the baseline measurement is defined as the measurement obtained predose on the first day of dosing.

8.8 Anti-SARS-CoV-2 Antibody Serology Testing

Participants will have serologic testing performed for the presence of anti-SARS-CoV-2 nucleocapsid (N) protein and neutralizing antibodies in serum at time points indicated in the SoA (Section 1.3.1).

Anti-nucleocapsid antibodies will be measured at the central laboratory using the Roche Elecsys Anti-SARS-CoV-2 test that is currently available under EUA. This assay is a qualitative test yielding a positive versus negative result for anti-nucleocapsid antibodies.

Anti-SARS-CoV-2 neutralizing antibody titers will be measured at a centralized testing laboratory using a VSV pseudotype containing a luciferase reporter and bearing a cytoplasmic domain-truncated SARS-CoV-2 spike protein. This assay, validated at Nexelis Laval Canada (a Q² Solutions Company), measures the ability of antibodies in serum to neutralize infection of a VSV reporter virus pseudotyped with the SARS-CoV-2 spike protein [Bewley, K. R., et al 2021].

8.9 Biomarkers

Biomarkers will not be evaluated in this study.

8.10 Future Biomedical Research Sample Collection

If the participant provides documented informed consent for FBR, the following specimens will be obtained as part of FBR:

- DNA for future research
- Leftover isolates from NP swab for viral testing/quantification stored for future research
- Leftover serum from anti-SARS-CoV-2 antibody serology testing stored for future research

8.11 Visit Requirements

Visit requirements are outlined in Section 1.3. Specific procedure-related details are provided in Section 8.

8.11.1 Infection Prevention Procedures

Each site will follow their institutional procedures and/or local requirements to protect study staff and other patients from infectious exposure to SARS-CoV-2. These procedures may include, but are not limited to:

- Provision of PPE to site staff, participants, and legally acceptable representatives
- Performing home visits, visits to alternate sites, or virtual visits (as allowed per the SoA)
- Designating special entry points for study participants for clinic visits

8.11.2 Types of Study Visits

8.11.2.1 Screening/Rescreening Visits

Screening

Screening of potential participants and index cases will occur within 5 days prior to randomization of the participants. The sample for the first detectable SARS-CoV-2 test for the index case must have been collected within 5 days prior to randomization of the participants. In addition, COVID-19 symptom onset for the index case may be no earlier than 5 days prior to randomization of the participants.

Prior to randomization, potential participants will be evaluated to determine that they fulfill the entry requirements as set forth in Section 5. Participants are expected to enroll as soon as possible after eligibility is confirmed.

Rescreening

Participants are allowed to rescreen 1 time. Rescreening procedures must be completed within 5 days from the time of sample collection for the first detectable SARS-CoV-2 test result of the index case and also within 5 days from the time of onset of symptoms for the index case. The following assessments must be repeated for participants who are rescreened:

- Vital signs and directed physical examination
- Review medical history and prior/concomitant medications for new information
- Local laboratory assessments for inclusion/exclusion (results within 5 days prior to randomization may be used for eligibility)
- Urine or serum β -hCG (pregnancy testing for WOCBP)

• Review of AEs

If the informed consent form has been updated, participants should be reconsented before rescreening. If no updates have been made, the informed consent from the original screening period should be reviewed with the participant and a verbal reconsent to continue in the study should be documented.

8.11.2.2 Clinic Visits, Home Visits, or Visits to an Alternate Site

If circumstances do not support a clinic visit, a home visit by the site personnel or a qualified health care provider (eg, home health care company, visiting nurse, etc) or a visit to an alternate site may be appropriate to perform study assessments and procedures per the SoA (where available and when permitted by local regulations and IRB/IEC). All study procedures indicated in the SoAs (Section 1.3.1 and Section 1.3.2) should be completed. The documentation from the visit will be provided to the investigator or medically qualified designee (consistent with local requirements) for review and assessment per institutional standards.

Every attempt should be made to assess the participant for a COVID-19 Confirmation Visit. See Section 8.2.3 for scheduling and visit requirements for a COVID-19 Confirmation Visit.

Refer to the procedure manual and/or the Investigator Trial File Binder (or equivalent) for additional details.

8.11.2.3 Virtual Visits

For participants, the investigator or designee may conduct a virtual visit (eg, by telehealth, telephone, webcast, videoconference, etc) for the Day 21 visit. When a virtual visit is listed in the SoA (Section 1.3.1), a clinic or home visit is not required. The choice to conduct a virtual visit, rather than a clinic or home visit/visit to an alternate site, is at the investigator's discretion. All study procedures indicated in the SoA (Section 1.3.1) should be completed.

For index cases who do not provide documented informed consent/assent for the optional NP or OP swab for viral testing/quantification, a virtual visit may be conducted for screening (Visit 1) procedures in the SoA (Section 1.3.2).

Identity of each participant and index case should be confirmed according to institutional procedures and/or local guidelines prior to conduct of virtual visits.

8.11.3 Participants Who Discontinue or Withdraw

Participants who discontinue study intervention prior to completion of the treatment period should complete the activities for the EOT visit at the time of discontinuing study intervention. The participant should then be encouraged to complete all the remaining subsequent study visits after EOT as outlined in the SoA (Section 1.3.1). If an active condition requires ongoing monitoring (eg, abnormal laboratory results, AEs, or progression

of COVID-19 symptoms), unscheduled visit(s) may be performed prior to the next study visit on Day 14.

Study activities for participants who withdraw from the study depend on the time of withdrawal, as follows:

- Participants who withdraw from the study prior to completion of the treatment period should complete the activities for the EOT visit at the time of withdrawal.
- Participants who withdraw from the study after the EOT visit, but prior to the Day 14 visit should complete all activities scheduled for the Day 14 visit, including the NP swab collection for RT-PCR testing at the central laboratory, at the time of withdrawal.
- Participants who withdraw from the study after the Day 14 visit should be encouraged to complete all applicable activities scheduled for the Day 29 visit at the time of withdrawal.

This visit at the time of study withdrawal should be conducted at the clinic or as a home visit if possible. If circumstances do not support an in-person visit, a virtual visit may be used; in this case, laboratory or other in-person measures would not be collected. Return of participant diaries and reconciliation of any study intervention should be coordinated if relevant. Any AEs that are present at the time of withdrawal should be followed in accordance with the safety requirements outlined in Section 8.4.

Both hospitalization and survival status at Day 29 are required for all randomized participants and should still be reported for participants who withdraw from the study where permitted by local guidelines.

9 STATISTICAL ANALYSIS PLAN

This section outlines the statistical analysis strategy and procedures for the study. If after the study has begun, but prior to any unblinding/final database lock, changes are made to the primary hypothesis, or the statistical methods related to this hypothesis, then the protocol will be amended (consistent with ICH Guideline E-9). Changes to exploratory or other non-confirmatory analyses made after the protocol has been finalized, but prior to unblinding/final database lock, will be documented in an sSAP and referenced in the CSR for the study. Post hoc exploratory analyses will be clearly identified in the CSR. Other planned analyses (ie, medical resource utilization outcomes and research plasma samples) are beyond the scope of this document or will be documented in separate analysis plans.

9.1 Statistical Analysis Plan Summary

Key elements of the statistical analysis plan are summarized below; the comprehensive plan is provided in Section 9.2 to Section 9.12.

Study Design Overview	A Phase 3, Multicenter, Randomized, Double-blind, Placebo- controlled Study to Evaluate the Efficacy and Safety of MK-4482 for the Prevention of COVID-19 (Laboratory-confirmed SARS- CoV-2 Infection With Symptoms) in Adults Residing With a Person With COVID-19.		
Treatment Assignment	 Approximately 1376 participants (regardless of SARS-CoV-2 results in baseline NP swabs) will be randomized in a 1:1 ratio (stratified per Section 6.3.2) to receive either MOV or placebo, Q12H for 5 days. MOV 800 mg (n~688) Placebo (n~688) 		
Analysis Populations	Efficacy: mITT Safety: APaT		
Primary Endpoint(s)	Efficacy: Percentage of participants with undetectable SARS-CoV-2 in baseline NP swabs developing COVID-19 through Day 14. Safety: AEs, and AEs leading to discontinuation of study intervention.		
Secondary Endpoints	 Percentage of participants (regardless of SARS-CoV-2 results in baseline NP swabs) developing COVID-19 through Day 14 Percentage of participants with undetectable SARS-CoV-2 in baseline NP swabs developing COVID-19 through Day 29. Percentage of participants with undetectable SARS-CoV-2 in baseline NP swabs having viral transmission through Day 14. Percentage of participants with detectable SARS-CoV-2 in baseline NP swabs having viral transmission through Day 14. Percentage of participants with detectable SARS-CoV-2 in baseline NP swabs developing COVID-19 through Day 14. 		
Statistical Methods for Key Efficacy Analyses			
Statistical Methods for Key Safety Analyses			

x / • • •	
Interim Analyses	One IA will be performed to evaluate safety and futility with respect to the primary efficacy hypothesis. Results will be reviewed by an eDMC. A summary of the IA is provided below. Further details are provided in Section 9.7.
	• Timing: To be conducted when approximately 55% of the participants with undetectable SARS-CoV-2 in baseline NP swabs have either completed the Day 14 visit or discontinued from the study prior to the Day 14 visit.
	• Testing: The primary efficacy hypothesis will be tested.
Multiplicity	A gatekeeping strategy will be used to control the overall FWER associated with the primary and secondary analyses.
	The following efficacy hypotheses will be tested sequentially at a one-sided 2.49% Type I error rate at final analyses:
	 Primary efficacy hypothesis (H1) testing superiority of MOV compared with placebo in participants with undetectable SARS-CoV-2 in baseline NP swabs through Day 14
	 Secondary hypothesis (H2) testing superiority of MOV compared with placebo in participants regardless of SARS-CoV-2 results in baseline NP swabs through Day 14
	The primary hypothesis (H1) will be tested first. The secondary hypothesis (H2) will be tested only if H1 is rejected. If H1 fails to reach statistical significance, then H2 will not be tested.
	Although there is no plan to stop the study early for efficacy at the interim analysis, a small statistical penalty (α =0.0001) will be applied for this interim analysis. The final analysis will be conducted at 0.0249 alpha-level to preserve the type I error level.
Sample Size and Power	The study will enroll approximately 1376 participants (regardless of SARS-CoV-2 results in baseline NP swabs; approximately 688 each in MOV 800 mg and in the placebo group). Assuming approximately 20% of the 1376 participants will have detectable SARS-CoV-2 at baseline [O'Brien, M. P., et al 2021], this will result in approximately 1100 participants with undetectable SARS-CoV-2 at baseline.
	The primary objective will be assessed on the approximately 1100 participants with undetectable SARS-CoV-2 in baseline NP swabs.
	Assume:
	• A background secondary attack rate of 8% and an underlying treatment difference (MOV minus placebo) in percentage of participants developing COVID-19 through Day 14 of -4.8 percentage points (a 60% relative reduction in attack rate).
	• At least 10% of the approximately 276 participants with detectable SARS-CoV-2 in baseline NP swabs are randomized to the MOV group.

The study has at least 90% power to demonstrate that MOV is
superior to placebo for prevention of confirmed COVID-19 in
household contacts (with undetectable SARS-CoV-2 in baseline
NP swabs) of an index case through Day 14 at an overall
one-sided 2.5% alpha-level.
Details are provided in Section 9.9.1.

9.2 Responsibility for Analyses/In-house Blinding

The statistical analysis of the data obtained from this study will be the responsibility of the Clinical Biostatistics department of the Sponsor or designee.

This study will be conducted as a double-blind study under in-house blinding procedures. The official, final database will not be unblinded until medical/scientific review has been performed, protocol deviations have been identified, and data have been declared final and complete.

The Clinical Biostatistics department will generate the randomized allocation schedule(s) for study intervention assignment.

Blinding issues related to the planned interim analysis are described in Section 9.7.

9.3 Hypotheses/Estimation

Objectives and hypotheses of the study are stated in Section 3.

9.4 Analysis Endpoints

Efficacy and safety endpoints that will be evaluated for within- and/or between treatment differences are listed below.

9.4.1 Efficacy Endpoints

The primary efficacy endpoint is the percentage of participants with undetectable SARS-CoV-2 in baseline NP swabs developing COVID-19 (laboratory-confirmed SARS-CoV-2 infection with symptoms) through Day 14.

The secondary efficacy endpoints are:

- Percentage of participants (regardless of SARS-CoV-2 results in baseline NP swabs) developing COVID-19 through Day 14
- Percentage of participants with undetectable SARS-CoV-2 in baseline NP swabs developing COVID-19 through Day 29
- Percentage of participants with undetectable SARS-CoV-2 in baseline NP swabs having viral transmission through Day 14

• Percentage of participants with detectable SARS-CoV-2 in baseline NP swabs developing COVID-19 through Day 14

The exploratory efficacy endpoints are:

- Percentage of participants (regardless of SARS-CoV-2 results in baseline NP swabs) developing COVID-19 through Day 29
- Percentage of participants with detectable SARS-CoV-2 in baseline NP swabs developing COVID-19 through Day 29
- Percentage of participants with undetectable SARS-CoV-2 in baseline NP swabs having viral transmission through Day 29
- Percentage of baseline seronegative participants with undetectable SARS-CoV-2 in baseline NP swabs developing anti-SARS-CoV-2 antibodies through Day 29
- Severity of laboratory-confirmed COVID-19 through Day 29 using NIAID ordinal scale criteria
- Participant-reported symptoms severity (for specified COVID-19 symptoms) in participants who develop laboratory-confirmed COVID-19 on or before Day 14
- Change from baseline in SARS-CoV-2 RNA titer and percentage of participants with undetectable SARS-CoV-2 RNA in NP swabs at Day 14 in participants with detectable SARS-CoV-2 in NP swabs at baseline
- Viral RNA mutation rate and detection of treatment-emergent sequence variants as assessed by comparison of viral gene sequencing at baseline and postbaseline in participants who develop laboratory-confirmed COVID-19 on or before Day 14
- Percentage of participants who develop laboratory-confirmed COVID-19 on or before Day 14 utilizing health care related to COVID-19 through Day 29
- Generic health-related quality-of-life in participants through Day 29 via EuroQoL Five Dimension Questionnaire (EQ-5D-5L)

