NP Swabs ^f for Viral Testing/Quantification		Х	Х	Х		Х	Х	 NP swabs at the Day 1, Day 5, Day 14, and Day 29 visits should be collected from all participants. NP swabs for confirmation of COVID-19 should be collected from all participants who develop qualifying symptoms of COVID-19 through Day 29. NP swab must be collected by site personnel or medically qualified designee. If an additional sample is collected for testing per local guidelines, the swab sample for central laboratory testing should be collected first.

Study Period:	Screening	Inter	vention		Fo	llow-up	Notes	
Visit Number/Name:	1 ^{a,b}	2 ^{a,b}	3	4	5	6	COVID-19 Confirmation Visit ^c	
Scheduled Day (Window)	(≤5 days prior to rand)	Day 1	Day 5 (+2 days) EOT	Day 14 (+3 days)	Day 21 (+3 days)	Day 29 (+3 days) LFU		
Type of Visit	C ^d	C ^d	C d	C ^d	V ^e	C ^d	C ^d	C = Clinic Visit V = Virtual Visit
Prophylaxis Outcome Assessment				Х		Х	Х	Assess for all participants whether a clinical success (no laboratory-confirmed COVID-19), failure (laboratory-confirmed COVID-19), or indeterminate. At the COVID-19 Confirmation Visit, assess only for participants who develop laboratory-confirmed COVID- 19 with symptoms. See Section 8.2.6.
Hospitalization Status			Х	Х	Х	Х		Collect from all participants.
Survival Status						Х		Collect from all participants.
Health care Utilization for COVID-19			X	Х	Х	Х	Х	Collect only from participants with laboratory-confirmed COVID-19.
Assessment for Severity of COVID-19 (NIAID Scale)			X	Х	Х	X	х	Collect only from participants with laboratory-confirmed COVID-19.
EuroQoL EQ-5D-5L Questionnaire		Х	X	Х		Х		Collect from all participants.
Safety Procedures								
Directed Physical Examination	Х	Х	Х				Х	Including height and weight at screening only
Vital Signs	Х	Х	Х	Х			Х	Heart rate, blood pressure, respiratory rate, temperature.

Study Period:	Screening	Inter	vention		Fo	llow-up	Notes	
Visit Number/Name:	1 ^{a,b}	2 ^{a,b}	3	4	5	6	COVID-19 Confirmation Visit ^c	
Scheduled Day (Window)	(≤5 days prior to rand)	Day 1	Day 5 (+2 days) EOT	Day 14 (+3 days)	Day 21 (+3 days)	Day 29 (+3 days) LFU		
Type of Visit	C ^d	C ^d	C ^d	C ^d	V ^e	C ^d	C ^d	C = Clinic Visit V = Virtual Visit
Blood Collection for Local Laboratory Evaluation	X ^g							

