• To evaluate the efficacy of MOV compared with placebo for the prevention and laboratory-confirmed COVID-19 through Day 29 in participants regardless of SARS-CoV-2 results in baseline NP swabs.	COVID-19 (laboratory-confirmed SARS-CoV-2 infection with symptoms)		
• To evaluate the prevention of viral transmission through Day 29 for MOV compared with placebo in participants with undetectable SARS-CoV-2 in baseline NP swabs.	• SARS-CoV-2 RNA		
• To evaluate the development of anti- SARS-CoV-2 antibodies through Day 29 in MOV recipients compared with placebo in baseline seronegative participants with undetectable SARS- CoV-2 RNA in baseline NP swabs.	Anti-SARS-CoV-2 antibodies		
• To evaluate the severity of laboratory- confirmed COVID-19 through Day 29 for MOV recipients compared with placebo recipients.	 NIAID ordinal scale criteria for COVID-19 severity 		
• For participants who develop laboratory- confirmed COVID-19 on or before Day 14, to describe the severity and/or presence of COVID-19 symptoms for MOV recipients compared with placebo recipients through resolution of symptoms or Day 29, whichever is first.	• Participant-reported symptoms severity (for specified COVID-19 symptoms)		
• For participants with detectable SARS-CoV-2 in NP swabs at baseline, to evaluate the antiviral activity of MOV compared with placebo as assessed by the change from baseline in SARS-CoV-2 RNA titer and percentage of participants with undetectable SARS-CoV-2 RNA in NP swabs at Day 14.	• Quantitative SARS-CoV-2 RNA		

C Confidential

16-OCT-2022

Objectives	Endpoints
• For participants who develop laboratory- confirmed COVID-19 on or before Day 14, to evaluate the effect of MOV on viral RNA mutation rate and detection of treatment-emergent sequence variants as assessed by comparison of viral gene sequencing in virus isolated at baseline and post-baseline in samples with evaluable SARS-CoV-2 RNA.	Viral RNA Sequences
• For participants who develop laboratory- confirmed COVID-19 on or before Day 14, to evaluate the prevention or reduction of health care utilization related to COVID-19 through Day 29 for MOV recipients compared with placebo recipients.	• Medically attended COVID-19

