For participants with laboratory-confirmed COVID-19, the severity of disease will be assessed using the NIAID ordinal scale for COVID-19 severity [Beigel, J. H., et al 2020]; see Section 8.2.10. The severity endpoint (exploratory) is included since it is conceivable that prophylactic treatment may be more effective at preventing onset of more severe disease than preventing the onset of symptomatic disease of any severity, particularly as some participants will enter the study with a detectable test for SARS-CoV-2 at baseline that is identified postrandomization. While most severity scales include criteria (eg, oxygen saturation criteria) that are not readily ascertained in an outpatient population living at home, the criteria for severe disease described in the NIAID ordinal scale include hospitalization as a basic criterion for moderate to severe disease, with an additional set of criteria (eg, supplemental oxygen requirements) to further delineate severity. These features of the NIAID ordinal scale

criteria for defining disease severity are readily applicable to a population that is mostly outpatient.

In addition to severity of disease, severity of symptoms will be collected from participants in the Symptom Diary to examine potential differences between prophylaxis with MOV or placebo, since prophylaxis may be more effective in preventing severe symptoms than in preventing the onset of any symptoms at all.

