8.2 Efficacy Assessments

8.2.1 Completing the Symptom Diary and Monitoring for Symptoms of COVID-19

Completing the Symptom Diary

Participants will self-report COVID-19 symptoms daily, if any, using a paper Symptom Diary. The Symptom Diary contains 15 targeted COVID-19 symptoms for which 13 will be assessed for absence/presence as well as severity (mild, moderate, or severe). Two other symptoms (loss of taste and loss of smell) will be assessed for absence/presence only. The recall period is "during the past 24 hours."

MK-4482-013-05 FINAL PROTOCOL

69

Targeted symptoms for COVID-19 assessed in the Symptom Diary include:

- Cough
- Sore throat
- Nasal congestion (stuffy nose)
- Runny nose
- Shortness of breath or difficulty breathing
- Muscle or body aches
- Fatigue (tiredness)
- Feeling hot or feverish
- Chills
- Headache
- Nausea
- Vomiting
- Diarrhea
- Loss of taste
- Loss of smell

The Symptom Diary will be completed by participants as follows:

- Participants will begin to complete the Symptom Diary on Day 1 (the same day as randomization), prior to the first dose of study intervention. Completion of the Day 1 Symptom Diary will be observed at the site (or a home visit, or visit to an alternate site) and documented, including time of participant completion, by study staff/qualified health care provider.
- After Day 1, participants should complete the Symptom Diary daily at approximately the same time every day through Day 29, recording the absence/presence of each symptom and highest severity (mild, moderate, or severe) for 13 of the 15 symptoms during the past 24 hours.

If the participant is able to comprehend the Symptom Diary questions (in the judgment of the investigator), but is unable to record their responses on the diary on their own per investigator judgment, collection of COVID-19 symptom data by study staff via an in-person

or virtual (eg, telephone) participant interview using a Sponsor-provided interviewer script should be implemented.

In the event of hospitalization, the Symptom Diary should be completed during hospitalization if possible. If the participant is unable to record their responses on the diary on their own, the Sponsor-provided interviewer script should be implemented by study staff. Completion of the diary should be resumed by the participant after discharge per the SoA, Section 1.3.1.

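### COVID-19 health care use is compared only among participants who became cases, so the comparison understates MOV's benefit if MOV prevents cases

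*Combined protocol and SAP*

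**What the plan says.** - **Endpoint.** Section 9.4.1 lists, among the exploratory endpoints, "Percentage of participants who develop laboratory-confirmed COVID-19 on or before Day 14 utilizing health care related to COVID-19 through Day 29". Read alone, this could mean a percentage of all participants.
- **Objective.** Section 3 settles the reading. The objective opens by restricting itself to participants who become cases by Day 14, and then sets out "to evaluate the prevention or reduction of health care utilization related to COVID-19 through Day 29 for MOV recipients compared with placebo recipients".
- **Aim.** Section 4.2.1.5 gives two reasons for measuring health care use: as an indirect marker of severity, and for a possible saving from giving prophylaxis to people without symptoms who are at high risk. The second concerns everyone randomized.
- **Data.** In the Schedule of Activities (1.3.1), the rows for health care use and NIAID severity carry the note "Collect only from participants with laboratory-confirmed COVID-19". Hospitalization status is collected from everyone.
- **Methods.** Section 9.6 defers exploratory methods to the sSAP. The opening of Section 9 puts medical resource utilization outside the document or in separate plans, and lets exploratory changes made before unblinding be documented in the sSAP.

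**The concern.** Case status by Day 14 arises after randomization and is the outcome that MOV is meant to change. Restricting the comparison to cases has two effects. It removes from the result the main way in which a prophylactic could save health care, namely that fewer people become ill. It also compares two groups that randomization no longer makes alike: the placebo cases, and those participants who became cases despite MOV.

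At stake is the reading of one exploratory result. A reader who takes the case-only percentages as the effect of prophylaxis on health care use would see too small a benefit and, under some conditions, an apparent disadvantage.

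**Working it through.** **Inputs from the plan (9.9.1, 9.9.2, balanced allocation).** Virus-negative at baseline: 550 per arm, attack rate 8% on placebo and 3.2% on MOV. Virus-positive: 138 per arm, 40% and 28%. The documents give no rate of health care use among cases, so every such rate below is an assumption.

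**Plan's own figures.** With these rates at one-sided 0.0249, the unpooled formula with the futility bound gives 93.3% power for 550 v 550 (Table 7: 93%). The pooled formula gives 95.6% for the balanced row of Table 8 (stated: 95%). The documents give no figure for the health care endpoint.

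**Expected cases.**
- Placebo: 550 × 0.08 + 138 × 0.40 = 44.0 + 55.2 = 99.2.
- MOV: 550 × 0.032 + 138 × 0.28 = 17.6 + 38.64 = 56.2.
- Case risk ratio: 17.6/44 = 0.40 virus-negative; 56.24/99.2 = 0.567 overall.
- Virus-positive share of cases: 55.2/99.2 = 55.6% on placebo, 38.64/56.24 = 68.7% on MOV. The case groups differ in mix as well as size.

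**Identity.** Let U be the number using care among these cases, C the number of cases and n the participants per arm. Then

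(U_MOV/C_MOV) / (U_pbo/C_pbo) = [(U_MOV/n) / (U_pbo/n)] ÷ [(C_MOV/n) / (C_pbo/n)].

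So the case-only ratio is the all-participant ratio divided by the case ratio. The multiplier is 1/0.40 = 2.5 (virus-negative) or 1/0.567 = 1.76 (overall), whatever the rate of care use. The case-only ratio exceeds 1 when MOV reduces care use by less than 60% (virus-negative) or 43.3% (overall).

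**Illustrations, virus-negative, assuming 30% of placebo cases are medically attended** (13.2 attended, 30.8 not):

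| Assumption | Case-only, MOV v placebo | All participants, MOV v placebo |
|---|---|---|
| MOV prevents 70% of attended and 35% of other cases | 16.5% v 30% | 0.72% v 2.40% |
| Attended cases cut by 70%, all cases by 60% | 22.5% v 30% | 0.72% v 2.40% |
| Attended cases cut by 50%, all cases by 60% | 37.5% v 30% | 1.2% v 2.4% |

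Row 1: 13.2 × 0.30 = 3.96 attended and 30.8 × 0.65 = 20.02 other, 23.98 cases in all. 3.96/23.98 = 16.5%; 3.96/550 = 0.72%. The ratios are 0.55 case-only and 0.30 over all participants. Here cases fall by 45%, not the plan's 60%. Row 2 keeps the plan's 60%: 0.30/0.40 = 0.75. Row 3: 0.50/0.40 = 1.25, a reversal.

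**Mix alone, whole population.** Assume the same care use in both arms, given baseline viral status. With 10% in virus-negative and 30% in virus-positive cases, case-only is 23.7% MOV v 21.1% placebo, while all-participant is 1.94% v 3.05%. With the rates swapped, case-only is 16.3% v 18.9%.

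**Precision of the case-only difference at 30% use.** 95% half-width, whole population: 1.96 × √(0.21/99.2 + 0.21/56.24) = 0.15. Virus-negative only: 1.96 × √(0.21/44 + 0.21/17.6) = 0.25.

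**The case against.** **The endpoint is exploratory and the methods are elsewhere.** It carries no alpha, and the sSAP or a separate resource-use plan may already contain an all-participant analysis. This stands as a limit on importance, and the absence of such an analysis cannot be shown from these documents. It does not remove the mismatch, because Sections 3 and 9.4.1 already name the subset.

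**A reader might infer that the planned comparison will make an effective drug look harmful.** The documents do not support that. Reversal needs care use to fall by less than cases do. Section 4.2.1.1 calls the other direction conceivable: that "prophylactic treatment may be more effective at preventing onset of more severe disease than preventing the onset of symptomatic disease of any severity". In that direction the result is attenuated and its sign is kept. With no care-use rate given, reversal is possible but not predicted.

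**A reader might infer that only about 18 v 44 cases are available, with a 25-point half-width.** Those are virus-negative counts, and neither the objective nor the endpoint is limited to that group. Over the whole population it is about 56 v 99 cases and 15 points.

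**A reader might extend the criticism equally to symptom and NIAID severity.** The 9.4.1 symptom endpoint is also confined to cases, but its objective is only "to describe the severity and/or presence of COVID-19 symptoms for MOV recipients compared with placebo recipients through resolution of symptoms or Day 29". For NIAID severity, collection is case-only but no analysis denominator is stated, so ranking non-cases lowest remains open.

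**An all-participant version is not entirely free.** Symptomatic participants missing the confirmatory test are indeterminate (8.2.6) and are imputed as cases in the primary analysis (Table 4), yet their health care use is not collected. This objection stands and shapes the fix.

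**Conclusion.** The point holds for the health care use objective and endpoint. On the plan's attack rates, the case-only risk ratio is 2.5 times (virus-negative) or 1.76 times (overall) the ratio for everyone randomized, so it understates the benefit of assignment and does not answer the aim in Section 4.2.1.5. The factor rests on the assumed 60% and 43% case reductions and on balanced allocation, and it shrinks towards 1 if MOV prevents fewer cases. Whether the sign changes depends on care-use rates that the documents do not give. The point has no bearing on the primary or H2 conclusions: the benefit of not becoming a case is captured by the primary endpoint.

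**What to change.** In 9.4.1, or in the sSAP before unblinding:

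1. Define medically attended COVID-19 through Day 29 as a percentage of all mITT and of all mITT-VN participants, counting confirmed non-cases as having none.
2. State whether cases with onset on Days 15-29 count. The present endpoint excludes them, so dropping the Day 14 limit should be a declared choice.
3. State a rule, with a sensitivity analysis, for symptomatic participants missing the confirmatory test. Scoring them as no use and as use would bracket the result.
4. If NIAID or symptom severity is compared between arms, do so over all participants with no COVID-19 as the lowest category. The diary supports this for symptoms, since "participants should complete the Symptom Diary daily at approximately the same time every day through Day 29".
5. Keep the case-only tables as description, without between-arm inference.

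The cost is wording, one extra rule and some added analysis. No new data collection is needed for confirmed non-cases, who have no COVID-19 care use by definition. The gap for untested symptomatic participants remains and is handled by item 3.
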